7.3 Summary of baseline data and flow of patients

All continuous variables will be summarised using the following descriptive statistics: n (non-missing sample size), mean, standard deviation (SD), 1st quartile, median, 3rd quartile, maximum and minimum. The frequency and percentages (based on the non-missing sample size) of observed levels will be reported for all categorical variables. The number of patients and the flowchart of the study will be presented.

7.4 Primary outcome analysis

The first primary outcome analysis will be to describe outcomes of MPX in PLWHIV and in PrEP users in terms of severity of lesions, time to lesion resolution, hospitalization, death.

The rate of serious lesions will be estimated by dividing the number of participants with serious lesions by the total number of participants in the full analysis population. Unadjusted and adjusted odds ratios (ORs) will be calculated using the logistic regression model to assess the impact of HIV on the occurrence of serious lesions compared to PrEP users.

Because some participants' lesion may not be healed by the end of the study period and, therefore, the duration of resolution would not be known, and thus right-censored, survival analysis methods such as the Kaplan-Meier and Cox model will be used to assess the time to lesion resolution. Kaplan-Meier estimates will be used to estimate the median time to lesion resolution. Unadjusted and adjusted hazard ratios (HR) will be estimated using the Cox proportional hazard model to assess the impact of HIV-infection on the time to lesion resolution compared with PrEP users.

The hospitalization rate will be estimated by dividing the number of participants hospitalized for mpox infection by the total number of participants in the total analysis population. Unadjusted and adjusted odds ratios (ORs) will be calculated using the logistic regression model to compare hospitalization rates between PLWHIV and PrEP users.

The mortality rate will be estimated using the Kaplan-Meier Method. Unadjusted and adjusted hazard ratios (HR) will be calculated using the Cox proportional hazard model to compare the rates of mortality between PLWHIV and PrEP users.

Adjustment variables will include the following potential confounders: Age (<30 vs 30-40 vs >40 years); Sex at birth (female vs male); Comorbidities; multiple sexual partners (yes vs no); number of sexual partners in the last 3 months prior to mpox diagnosis; and smallpox vaccination history (yes vs no).

The second primary outcome analysis will be performed between PLWHIV with MPX versus PrEP users with MPX. The endpoint is to assess differences in clinical manifestations of MPX between the groups. Unadjusted and adjusted odds ratios (ORs) will be calculated using the logistic regression models to compare the rates of clinical manifestations between PLWHIH and PrEP users. The adjusted variables will be the following (potential confounders): Age (<30 vs 30-40 vs >40 years); Sex at birth (female vs male); Comorbidities; multiple sexual partners (yes vs no); number of sexual partners in the last 3 months prior to MPX diagnosis; and smallpox vaccination history (yes vs no).

The third primary outcome analysis will be performed within the PLWHIV group. The endpoint is to evaluate the characteristics of HIV infection associated with severe mpox. Univariable and multivariable logistic regression models will be used to assess factors associated with severe mpox in PLWHIV. The following variables will be evaluated: time since HIV diagnosis (years); current ART; CDC disease stage; CD4 cell nadir; last CD4 cell count/HIV-RNA before MPX diagnosis (including CD4% and CD4/CD8 ratio). Variables achieving $P < 0.20$ in the univariable analysis will be retained for the multivariable analysis.

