1 BACKGROUND

Mpox (or MPX) (previously known as Monkeypox) is an acute febrile rash illness caused by the mpox virus, an orthopox virus related to variola virus (causative agent of smallpox), cowpox virus and the vaccine strain vaccinia virus.

Since the first identification of a mpox infection in humans in 1970, the majority of human cases have been reported from Africa, including sporadic outbreaks that usually resulted from contact with wildlife reservoirs, in particular rodents. Animal-to-human (zoonotic) transmission can result from direct contact with the blood, bodily fluids, or cutaneous or mucosal lesions of infected animals. There are two distinct genetic clades of the mpox virus: the central African or Congo Basin clade (Clade 1) and the west African clade (Clade 2). The case fatality ratio of mpox has historically ranged from 0 to 11 % in the general population and has been higher among young children. In recent times, the case fatality ratio has been around 3–6%. The central African (Congo Basin) clade has historically caused more disease and was thought to be more transmissible. (WHO fact sheet) Human-to-human transmission can result from close contact with respiratory secretions, skin lesions of an infected person or recently contaminated objects. Transmission via droplet respiratory particles usually requires prolonged face-to-face contact. (WHO fact sheet) Cross-immunity exists between different orthopox viruses, and, in the past, vaccination against smallpox was protective against mpox infection. However, the global smallpox vaccination campaigns were discontinued after eradication of the disease, likely leaving the population below 40 to 50 years of age (depending on the country) more susceptible to mpox.

Mpox is usually a self-limited disease with the symptoms lasting from 2 to 4 weeks. Severe cases occur more commonly among children and are related to the extent of virus exposure, patient health status and nature of complications. Underlying immune deficiencies may lead to worse outcomes. Complications of mpox can include secondary infections, bronchopneumonia, sepsis, encephalitis, and infection of the cornea with ensuing loss of vision.

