2 RATIONALE

We have few data to suggest whether or not People Living with HIV (PLWHIV) are at an increased risk of serious illness or death or there is an impact of being HIV positive on outcomes or clinical presentation or if there is any dependence on CD4 cell count and viral load.

The most affected countries in Europe include Spain, the United Kingdom, Germany, France and the Netherlands. The majority of the cases identified to date have been among men who have sexual activity with men (MSM). There has been a preponderance of genital, perianal and mucosal lesions, rather than the centrifugal rash classically described for mpox. An early report indicates that 95% of patients had a rash, 73% had anogenital lesions and 41% had mucosal lesions. Some of the lesions persist for a long period and some patients have required hospitalisation for pain management or treatment of secondary skin infections. 13% of the patients were hospitalized. Reasons for hospitalization included pain management (mostly severe anorectal pain), soft-tissue superinfection, pharyngitis limiting oral intake, eye lesions, acute kidney injury, myocarditis and/or infection-control purposes. In this report, 98% were MSM and 41% had HIV infection. (Thornhill *et al.* NEJM 2022)

Rapid data collection and analysis about MPX in PLWHIV will depend on international multi-centre collaborations, for which NEAT ID has a strong expertise. The majority of PLWHIV in Europe are in routine clinical care, allowing for a comprehensive data collection about MPX and studying the impact of HIV drugs and specific risk factors. The NEAT ID MPX Coinfection Dashboard was established in August 2022 to collect data on the number of PLWHIV co-infected with MPX and anonymised, aggregated data from this dashboard on 249 PLWHIV who attended Chelsea and Westminster Hospital between May 15th and December 15th 2022 were recently presented at the CROI 2023 conference ([name] *et al*, CROI 2023). It has provided evidence that a significant number of PLWHIV were suffering from MPX in Europe at that time and that these individuals can be enrolled into an Epidemiology and Real-World- Data study.

A feasibility study of HIV negative patients receiving Pre-exposure prophylaxis (PrEP) across the NEAT ID network has identified 45 sites that provide PrEP services for a total of 27,416 PrEP users with 1,361 new PrEP initiators each month.

There are two central questions to address:

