6 STUDY PROCEDURES

6.1 Participant Identification

Most People living with HIV (PLWHIV) and HIV negative PrEP users will be identified from sites in the NEAT ID network. PLWHIV are routinely followed-up at specialised outpatient clinics with regular follow up visits as standard of care and many of these centres take care of patients on PrEP. Patients are taking PrEP to prevent contraction of HIV as they perceive themselves to be at risk due to frequent sexual activity with different partners.

In July 2022, NEAT ID opened a dashboard to 150 sites from 20 countries to provide basic information about the number of PLWHIV with MPX and disease outcomes at their centres (<https://www.NEAT-ID.org/>). Data were provided from patients' cases from April 2022 until November 2022 from 31 global sites, 26 sites from 16 European countries and 5 site in Latin America. The dashboard provided a first estimate about the total numbers of PLWHIV with MPX and where these patients are in continued care. As of the end of November 2022, 907 PLWHIV with MPX were reported in care, with 53 hospitalisations and 1 death from an estimated number of 85,279 PLWHIV in routine care at these sites ([name] *et al*, EACS 2023). These case numbers strongly suggested feasibility to recruit sufficient numbers of PLWHIV with MPX and that patients have been identified at their centres already.

A feasibility study of patients receiving PrEP across the NEAT ID network have identified 45 sites that provide PrEP services for a total of 27,416 PrEP users with 1,361 new PrEP initiators each month.

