6.2 Data collection

Only real-world retrospective data will be used for this study. Patients who have had mpox and fulfil the entry criteria will be enrolled after 90 days from date of diagnosis to allow for follow up data to be collected. Pseudonymised retrospective data will be transcribed into the eCRF system from source data at each clinical site or from existing cohort databases, where appropriate. No personal identifiable data will be transmitted to NEAT ID. The data elements will be transcribed from source data according to the data collection list below. Mechanisms to ensure data quality and integrity will be deployed as per applicable standard operating procedures and in line with Good Documentation Practice (GDocP) and Good Pharmacoepidemiology Practice (GPP). Patients will be identified and documented by participating sites.

For all patients with MPX the following information will be collected where routinely available:

- Age (year of birth)
- Sex and gender identity
- Ethnicity (where available)
- HIV status
- HIV pre-exposure prophylaxis (PrEP) use
- Comorbidities and Medical history (diabetes mellitus, other immunosuppression (e.g. solid organ transplant), known chronic kidney or liver disease, mental health conditions)
- Recent sexual history (3 months) – number of recent partners
- Recent and/or concomitant sexually transmitted infections
- Orthopoxvirus vaccination history (if available)
- Symptom onset date (fever onset, lesion onset, rectal pain)

- Date of positive PCR test result (documented)
- MPX severity -Reported clinical signs and symptoms of mpox (e.g. rash, mouth lesions, rectal pain, breathlessness)
- Time to resolution of lesions, if known
- Mortality as a consequence of MPX including cause
- Hospitalisation for MPX and length of hospitalisation
- Drug treatment for MPX (Tecovirimat, other)
- Drug for complications associated with MPX (laxatives, antibiotics, analgesia)
- recent travel to/living in endemic country or country with outbreak
- contact with suspected, probable, or confirmed case (if known)
- contact with infected animal (if known)

For PLWHIV the following additional information will be collected:

- Date of HIV diagnosis
- Current Antiretroviral Therapy/Treatment (ART)
- If not on ART, reason for not being on ART
- Last CD4 cell count (including CD4% and CD4/CD8 ratio) and
- Last HIV-RNA before MPX diagnosis

Skin lesion at peak severity score:

- Not presenting with skin lesions (0 skin lesions)

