7.7 Procedure(s) to account for missing or spurious data

Multiple imputation using Chained Equations approach (MICE) will be used to fill in missing data. Ten imputations (M=10) will be chosen to obtain valid inference and reduce sampling variability resulting from the imputation process. Variables with a missing rate above 20% will be excluded and the outcomes will be included in the imputation model. All 10 datasets will be analyzed and combined using Rubin rules. A complete case analysis will also be performed as a sensitivity analysis to assess the robustness of the results.

8 Consent

Due to the nature of this data collection study, consent will not be sought.

In order to maintain confidentiality, the participant will be identified only by subject number. Participant data will be collected from electronic health records by appropriately trained and authorised member(s) of the study team who must be identified and authorised in writing by the Principal Investigator (PI). A delegation of responsibility log will be updated accordingly.

As data collection is entirely retrospective, participants will not need to attend any additional visits. Participants will not have undergone any procedures above their routine standard of care.

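### Section 7.4 does not separate unhealed lesions from healed lesions with no recorded date; if the latter are censored at 3 months, healing time is overstated and the HIV comparison can be distorted

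*Combined protocol and SAP*

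**What the plan says.** Section 7.4 analyses time to lesion resolution under the first primary outcome, although section 3.4 lists it as a secondary endpoint. The reason given for survival methods is that a participant's "lesion may not be healed by the end of the study period", so that "the duration of resolution would not be known, and thus right-censored". Then "Kaplan-Meier estimates will be used to estimate the median time to lesion resolution", and a Cox model compares PLWHIV with PrEP users.

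Other sections bear on this:

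- Section 1: "Mpox is usually a self-limited disease with the symptoms lasting from 2 to 4 weeks". Section 2 adds: "Some of the lesions persist for a long period", with no share given.
- Section 4 ends case data at clinical resolution, with lesion resolution, hospital discharge and death as examples, and a limit of 3 months. Section 5.1 requires diagnosis more than 90 days before data collection.
- Section 6.2 collects "Time to resolution of lesions, if known". It lists no date of a last examination with lesions and no date of a first contact without them.
- Section 7.2 puts every primary and secondary endpoint on the full analysis population.
- Section 7.7: "Multiple imputation using Chained Equations approach (MICE) will be used to fill in missing data". It also excludes variables with more than 20% missing, puts outcomes in the imputation model, and adds a complete-case sensitivity analysis. It does not say whether any of this covers the healing date.

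**The concern.** There are two kinds of patient without a healing date: those still unhealed when observation ends, and those who healed without anyone recording when. Section 7.4 recognises only the first. Given the usual length of illness and the 90-day gap before data collection, the second kind is likely to supply many of the unknowns, and perhaps most.

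For these patients the analyst has three routes: censor at the end of the window, impute under section 7.7, or drop them. The plan does not choose. The first route counts a healed patient as at risk and unhealed for weeks after healing. That lengthens the Kaplan-Meier median, leaves a false plateau of unhealed patients, and weakens any true HIV effect. If documentation differs between the groups, the hazard ratio also reflects how often patients return to clinic. Section 6.1 makes a difference plausible: "PLWHIV are routinely followed-up at specialised outpatient clinics with regular follow up visits as standard of care", while section 5.1 admits PrEP users who obtain PrEP themselves. Better documentation in PLWHIV would hide slower healing in that group; worse documentation would create it.

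**Working it through.** The plan states no expected healing time, unknown share, effect size or event count for this endpoint, so there is no figure of its own to reproduce. The check asks what happens if undocumented healers are censored at day 90.

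**Inputs from the documents.** Illness of 14 to 28 days (section 1); a window of up to 3 months (section 4); about 2000 patients (section 4); a 41% HIV share in the cited early report (section 1), used only as an alternative group split.

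**Assumptions.** Two lognormal healing distributions: A, with 5th and 95th percentiles at 14 and 28 days (median √(14 × 28) = 19.8 days); B, with median 21 days and log-SD 0.4. Unknown share *u* of 5% to 40%. Group split 50:50 or 41:59. Two-sided 5% test.

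**Step 1: how many are truly unhealed at day 90?** Under B, z = ln(90/21)/0.4 = 3.64, so the probability is about 0.014%; under A it is negligible. If healing follows either distribution, almost every censored case is an undocumented date. Persistent lesions, as mentioned in section 2, would raise this by an unknown amount.

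**Step 2: Kaplan-Meier median.** With a share *u* censored after all observed healing, S(t) = u + (1 − u)·S_true(t). The median lies where F_true(t) = 0.5/(1 − u). For *u* = 30%, F = 0.714, z = 0.566, and under B t = 21 × exp(0.4 × 0.566) = 26.3 days.

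| Unknown | Median A (days) | Median B (days) |
|---|---|---|
| 0% | 19.8 | 21.0 |
| 10% | 20.4 | 22.2 |
| 20% | 21.2 | 23.9 |
| 30% | 22.3 | 26.3 |
| 40% | 24.3 | 30.9 |

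From 50% unknown the median is not reached.

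**Step 3: hazard ratio with no true HIV effect.** Let u1 be the unknown share in PLWHIV and u2 that in PrEP users. When the true unhealed proportion is S, the apparent hazard ratio is [(1 − u1)/(u1 + (1 − u1)S)] ÷ [(1 − u2)/(u2 + (1 − u2)S)]. For 10% v 20% it is 0.9/0.8 = 1.125 at the start, 1.23 when half have healed, and 9/4 = 2.25 at the end. The artefact is therefore also non-proportional. The Cox model averages it. Solving the Cox score equation for its large-sample value at a 50:50 split, with rejection rates from simulation at N = 2000, gives:

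| Unknown, PLWHIV v PrEP | Cox HR | False rejection |
|---|---|---|
| 20% v 20% | 1.00 | 4–8% |
| 15% v 20% | 1.14 | 66–76% |
| 10% v 20% | 1.30 | 100% |
| 5% v 15% | 1.33 | not run |
| 10% v 30% | 1.67 | 100% (B) |
| 20% v 10% | 0.77 | 100% |

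With a common healing curve and censoring after all events, only the order of events matters, so these HRs do not depend on A or B. The 41:59 split changes them by at most 0.01. Separate simulations of 10% v 30% gave 1.65 to 1.67.

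**Step 4: a true effect.** Suppose healing takes 10% longer in PLWHIV. The HR with all dates known is 0.66 (A) or 0.80 (B). At 20% unknown in both groups it becomes 0.82 or 0.91. At 10% v 20% it becomes 1.04 or 1.16, so the harm is masked or reversed.

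**Step 5: other handling, no true effect.**

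- Censoring at a last visit with lesions, placed at random before healing: HR 1.02–1.04 for 10% v 20% (rejection 6–13%) and 1.06–1.09 for 10% v 30% (rejection 19–37%).
- The same, with the last visit in the second half of the healing time: HR 1.14 for 10% v 30%.
- Censoring at a visit unrelated to healing, or dropping unknowns that are missing at random: HR about 1.00.

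**The case against.** A reader might infer that the plan counts an unknown date as not healed. It does not say so. The sentence in section 7.4 runs from unhealed, to unknown duration, to censored; the converse comes from a gap. Nor is day 90 the only possible censoring point: section 4 also names hospital discharge as an end of data collection, and section 7.5 uses last observation for length of stay, so the authors know that concept. The eCRF is not among the documents, and a field absent from section 6.2 may exist there.

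Section 7.7 could also catch the problem. A complete-case analysis that drops unknown dates gives an HR of about 1.00 if they are missing at random. The 20% rule might remove the variable: 10% v 30% at a 41:59 split is 0.41 × 10 + 0.59 × 30 = 21.8% missing. But a time coded as censored is not missing, so a complete-case analysis would keep it, and exclusion would remove the endpoint.

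It is also tempting to read section 6.1 as showing that PrEP users are less well documented. The same passage says many centres also care for PrEP patients, and section 5 describes both groups as in routine follow-up at the sites. Unequal documentation is plausible but not shown. Right-censoring itself is not the error; the choice of date is.

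These points make the harm conditional. They do not supply the missing rule or the missing dates.

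**Conclusion.** The gap is real and should be closed. The plan does not distinguish unhealed from undocumented, sets no time origin or censoring date for healing, leaves the reach of section 7.7 open, and lists no dates from which correct censoring could be built. Dates not abstracted cannot be recovered at analysis.

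The size depends on two things that the documents leave open. If undocumented healers are censored at the end of the window, medians are too long whatever the group balance, and a true HIV effect is diluted. A false HIV effect arises only if the unknown shares also differ between groups; with equal shares the null HR stays at 1.00. A 10-point difference then gives an HR of about 1.3 or 0.77, depending on direction. The documents do not support the stronger conclusions that the plan will produce a false HIV difference, or that it must run in a particular direction.

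**What to change.** In section 6.2 and the eCRF, add two dates where recorded: the last assessment with lesions present, and the first contact with lesions resolved.

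In section 7.4:

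- State the time origin.
- Use the exact healing date when known. Otherwise treat healing as interval-censored between the two new dates.
- If no later contact documents resolution, censor at the last assessment with lesions present, not at the end of the window.
- State that the healing date is not imputed under section 7.7.
- Report the share with unknown healing by group.
- Add a sensitivity analysis that excludes unknown dates.

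The cost is two date fields from records already being abstracted, an interval-censored model alongside the planned Kaplan-Meier and Cox analyses, and slightly wider intervals. Some bias remains for patients never seen again after their last visit with lesions (HR up to about 1.14 in the worst scenario tested), because leaving care may itself reflect healing. Reporting the unknown share by group lets readers judge it.

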Full study Title:	Morbidity, Mortality And Risk Factors of Mpox in HIV negative high-risk Sexual health clinic attenders and People Living With HIV - MASH Study	
Short title/Acronym	MASH	
Clinical Phase	Observational Retrospective Cohort Study	
Study Design	Case-descriptive study	
Study Population	PLWHIV (people living with HIV) who are currently sexually active and HIV negative high-risk Sexual Health Clinic attenders (PrEP users) with Mpox	
End of study data collection	Date of clinical resolution e.g. lesion resolution, hospital discharge or death (up to 3 months)	
Planned Sample Size	Approximately 2000	
Eligibility Criteria	at least 18 years of age with either documented HIV-1 infection or PrEP clinic attenders, and confirmed MPX infection by documented result on PCR testing on skin and/or mucosal and/or any anatomical site.	
Indications	HIV & MPX; PrEP patients & MPX	
Methodology	Only real-world, routinely collected, retrospective data will be used for this study collected from patients who during the study period have had confirmed Mpox. Pseudonymised data will be transcribed into the eCRF (electronic Case Report Form) system from source data at each clinical site or from existing databases, where appropriate. No personal identifiable data will be transmitted to NEAT ID.	
Number of sites	Up to 12 sites in up to 7 countries	
Objectives	
Primary
 
 1. To describe and compare outcomes of MPX in PLWHIV and an HIV-negative population of people using pre-exposure HIV prophylaxis (PrEP users) 2. To identify risk factors for specific MPX outcomes (including CD4 cell count nadir and current CD4 count in PLWHIV) 	
Secondary
 
 1. To estimate the approximate prevalence of MPX in PLWHIV and PrEP users in this retrospective cohort 2. To describe clinical manifestation of MPX and response to MPX treatment in PLWHIV and PrEP users 3. To describe the co-morbidities in PLWHIV and PrEP users

Outcome Measures	Primary	Secondary

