Until recently, there have been very few travel-associated cases in non-African countries, with very limited onward transmission. However, following notification from the United Kingdom to WHO on the 15th of May 2022, of two confirmed and one probable case of mpox, person-to-person transmission of mpox has been increasingly observed in countries outside of Africa. By August 5th, 2022, 28,220 cases of mpox infection have been reported in 88 locations worldwide, 27,875 of whom in countries that have not historically reported mpox. The largest numbers of cases have been reported in Europe. (Joint ECDC-WHO Regional Office for Europe Mpox Surveillance Bulletin (europa.eu)) The viruses associated with these cases are most closely related to clade 2 but have some genetic differences and has been tentatively named Clade 3.

An early report indicates that patients in the epidemic outside Africa may present with a clinical picture that differs from the usual presentation. 95% of patients had a rash, 73% had anogenital lesions and 41% had mucosal lesions. 13% of the patients were hospitalized. Reasons for hospitalization included pain management (mostly severe anorectal pain), soft-tissue superinfection, pharyngitis limiting oral intake, eye lesions, acute kidney injury, myocarditis and/or infection-control purposes. In this report, 98% were Men who have sexual activity with men (MSM) and 41% had Human Immunodeficiency Virus (HIV) infection – these groups are currently considered at a higher epidemiological risk to contract the infection. (Thornhill e.a. NEJM 2022)

A vaccine campaign with vaccinia virus (smallpox vaccine) has been started for specific risk groups; this may impact the transmission of mpox virus, but clinical evidence is still lacking and available dosages are limited. Furthermore, it is feared that the epidemic may extend outside of the currently defined risk groups.

Currently, antiviral medication for mpox that has been properly evaluated in clinical trials is not available, but several antivirals have demonstrated activity in vitro and in animal models. The most promising is tecovirimat, an oral anti-viral drug that inhibits the cytopathic effect of mpox virus on cell cultures and reduces plaque formation. (Smith, AAC 2009) Furthermore, tecovirimat has been found to protect non-human primates, when administered at three days post challenge with lethal doses of mpox virus. (Jordan *et al.* AAC 2009).

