4 STUDY DESIGN

This is an observational retrospective cohort study.

In total, approximately 2000 cases from PLHIV and PrEP users will be analysed

Only real-world retrospective, routine data will be used for this study. Deidentified data will be transcribed into the Electronic Case Report Form (eCRF) system from source data at each clinical site or from existing cohort databases, where appropriate.

Case data will be collected until the Date of clinical resolution e.g. lesion resolution, hospital discharge or death (up to 3 months)

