7.2 Statistical analysis plan

This is primarily a descriptive retrospective data cohort study but will compare MPX severity between 1) PLWHIV and PrEP users, to show whether HIV infection is associated with more severe MPX; 2) PLWHIV with different characteristics, to identify factors associated with severe MPX within HIV infected population.

All enrolled participants who meet the eligibility criteria will be included in the analysis population (full analysis population). All primary and secondary endpoints will be performed with the full analysis population.

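### Section 7.4 plans adjusted Cox hazard ratios for death, but the network's own data imply about 2 deaths in 2000 patients (95% CI 0.06 to 12.3) against at least 8 model parameters

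*Combined protocol and SAP*

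**What the plan says.** Section 3.3 lists death among the primary outcomes. Section 7.4 sets its analysis: "The mortality rate will be estimated using the Kaplan-Meier Method. Unadjusted and adjusted hazard ratios (HR) will be calculated" by Cox regression, PLWHIV against PrEP users. The adjustment list that closes that part of 7.4 has age in three bands, sex at birth, comorbidities, multiple partners (yes/no), number of partners in the last 3 months, and smallpox vaccination. No expected number of deaths, minimum event count or sparse-data fallback is given.

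Two mortality figures appear elsewhere. Section 6.1 reports from the network's dashboard that, to the end of November 2022, "907 PLWHIV with MPX were reported in care, with 53 hospitalisations and 1 death". The Background says "In recent times, the case fatality ratio has been around" 3–6%.

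On follow-up, section 4 states: "Case data will be collected until the Date of clinical resolution e.g. lesion resolution, hospital discharge or death (up to 3 months"), and the synopsis agrees. The data list in 6.2 includes "Mortality as a consequence of MPX including cause", and both symptom-onset and PCR dates. Section 7.4 names neither date as time zero for death.

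Section 7.2 describes the aim: "This is primarily a descriptive retrospective data cohort study", with comparisons of severity added.

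**The concern.** A Cox model draws its information from events, not from patients. If the study sees about two deaths, a model with HIV status and six adjustment variables has more coefficients than events. It will then fail to converge, or return estimates driven by separation. Even the unadjusted hazard ratio is undefined whenever one group has no death.

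The plan commits to these analyses for a primary outcome without saying what happens if they cannot be fitted. The likely result is a change of method after the data are seen. That is worth avoiding, because an estimate that always works is already used elsewhere in the plan.

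**Working it through.** **The plan's own figure.** The only sample-size arithmetic is in section 7.1: about 170 patients per site at 12 sites. 2000/12 = 166.7 and 12 × 170 = 2040, so the figure reproduces. No event count, power or significance level is stated for death, so there is nothing further to reproduce.

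**Inputs.** N is about 2000 (synopsis, section 4). The mortality figure is 1/907 (section 6.1). The adjustment set is from 7.4. The group split is not stated; 1000 per group is assumed below.

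**Expected deaths, equal risk in both groups (assumption).**
- Rate: 1/907 = 0.110%, exact 95% CI 0.003% to 0.613%.
- Expected deaths: 2000 × 1/907 = 2.2, with limits 0.06 and 12.3 (sampling error only).
- Chance of no death at all at the point estimate: (1 − 1/907)^2000 = 0.11.

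**Parameters in the adjusted model (minimum).** HIV status 1, age 2, sex 1, comorbidities 1, multiple partners 1, number of partners 1, vaccination 1, total 8. Entering the four comorbidity groups of section 7.5 separately gives 11.

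**Events per parameter (8 parameters).** 2.2/8 = 0.28. At the upper limit, 12.3/8 = 1.5.

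**Unadjusted hazard ratio.** With p = 1/907 in PLWHIV and p/k in PrEP users, the probability that at least one group has no death is 1 − [1 − (1 − p)^1000] × [1 − (1 − p/k)^1000].

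| PrEP risk relative to PLWHIV | Expected deaths | P(no finite hazard ratio) |
|---|---|---|
| equal (k = 1) | 2.2 | 1 − 0.668 × 0.668 = 0.55 |
| half (k = 2) | 1.7 | 1 − 0.668 × 0.424 = 0.72 |
| one fifth (k = 5) | 1.3 | 1 − 0.668 × 0.198 = 0.87 |

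The lower rows are the direction of the study's own hypothesis in section 3. When an estimate exists it is very imprecise: with one death in each group, a hazard ratio of 1 has an approximate 95% CI factor of exp(1.96 × √(1/1 + 1/1)) = 16, that is 0.06 to 16.

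**The alternative.** 1/1000 gives 0.10% (exact 95% CI 0.003% to 0.56%); 0/1000 gives 0% (0% to 0.37%). Both can be reported. The Fisher test at 1000 v 1000 gives p = 0.50 for 2 v 0 deaths, 0.062 for 5 v 0 and 0.031 for 6 v 0.

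**The case against.** **One event is a thin basis.** This stands, and is why the interval matters more than 2.2. The dashboard covers PLWHIV only, drew on 31 sites rather than up to 12, and ends in November 2022. For the adjusted model the conclusion holds across the whole interval. For the unadjusted hazard ratio it is softer: averaging over the uncertainty in 1/907 lowers 0.55 to 0.48, and at 12.3 deaths an estimate would nearly always exist, with a CI factor of about 3 either side under a 1:1 split.

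**The Background figure of 3–6% would support a model.** It would give 60 to 120 deaths, or 7.5 to 15 per parameter. But it is general background. Even its lower end is nearly five times the network figure's upper limit of 0.61%, and 6.1 is the source the protocol uses for feasibility.

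**The dashboard may understate severity.** Its hospitalisation rate is 53/907 = 5.8%, while in the early report "13% of the patients were hospitalized". The 13% includes infection-control admissions, and nothing in the documents says that deaths scale with admissions. Scaling anyway by 13/5.84 = 2.2 gives 27 deaths at the upper limit, or 3.4 per parameter.

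**The harm is limited.** This also stands. The study is mainly descriptive and a failed model would be visible. A penalised unadjusted comparison, or an adjusted model fitted only above a pre-set event count, would also be defensible.

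**A stronger reading on follow-up is tempting.** A reader might infer that the passages on follow-up contradict each other, or that Kaplan-Meier mortality will be biased upward. The documents do not support either. Section 6.2 is a list of data items, and section 4 sets the cut-off for all case data. The 90-day rule in 5.1, 5.2 and 6.2 points to a window of about 3 months from diagnosis. Upward bias arises only if patients are censored for death at resolution; it disappears if all are followed to 3 months, and its size cannot be derived. What stays open is the time zero and whether vital status is taken after resolution.

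**Conclusion.** The adjusted Cox hazard ratio for death is not supportable: 0.28 expected events per parameter, and 1.5 at the upper confidence limit. The unadjusted hazard ratio is about as likely as not to have no finite estimate under equal risk, and more likely than not if HIV worsens outcome. These results rest on the network rate of 1/907 carrying over to the study sites, on PrEP users having the same risk or lower, on about 2000 patients, and, for the unadjusted result, on an assumed 1000 per group.

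This should be fixed. It would be wrong to infer that the primary analysis as a whole fails. At the dashboard rate, hospitalisations would number about 2000 × 53/907 = 117, or roughly 15 per parameter for the same 8 parameters (again assuming equal risk), so that model is not affected by this argument. The missing time origin and the open question of follow-up after resolution are minor.

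**What to change.** In section 7.4, replace the Kaplan-Meier and Cox analysis of death with deaths over N in each group, Clopper-Pearson 95% intervals, and a Fisher exact test or exact risk difference. State that mortality is read descriptively.

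Keep death as the outcome, since that is what 3.3 and 7.4 list. Report mpox-attributed deaths, the item in 6.2, alongside it; or else reconcile 3.3 and 7.4 with 6.2 explicitly. Attributed death should not replace death without comment.

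As a minor clarification, name the time origin (for example the PCR date, already collected) and say whether deaths are counted only to the existing end of data collection or to 3 months in every patient.

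Costs:
- There will be no adjusted mortality comparison.
- The Fisher test has little power: 6 v 0 deaths in 1000 v 1000 are needed for p < 0.05.
- Counting to 3 months in everyone could require vital status after resolution from records. Counting to the existing end point should not.
- The change alters protocol text, so it may need review as an amendment under section 10.1.
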